3. SYNOPSIS

51 511101 515				
Study Title	Abbreviated Magnetic Resonance Imaging vs ultrasound surveillance for liver cancer detection in people at high risk of developing liver cancer			
Internal ref. no. / short title	AMULET			
Study registration	NCT06658782			
Sponsor	University of Oxford Research Governance, Ethics & Assurance, [name] Email: [contact]			
Funder	National Institute	of Health Research and Medical	Research Council	
Study Design	Prospective cohor	t study		
Study Participants	People with cirrho	osis and high risk of Hepatocellula	ar cancer (HCC)	
Sample Size	300			
Planned Study Period	Duration of an individual participant's involvement: 30 months 1 st October 2024 – 30 th April 2039 (including 10 years passive follow up) No additional funding is required as we are only accessing records during the passive follow up phase.			
Planned Recruitment period	Recruitment start date: 1 st November 2024 Recruitment end date: 30 th April 2026			
		Outcome Measures	Timepoint(s)	
Primary Objective To evaluate the diagnostic performance of non-contrast enhanced MRI (nceMRI) and ultrasound scans (USS) as surveillance tools for the diagnosis of hepatocellular cancer (HCC).		True positive tests for HCC per round of surveillance False positive tests for HCC per round of surveillance Positive predictive value for HCC per round of surveillance True negative tests for HCC over the 30 months of surveillance False negative tests for HCC over the 30 months of surveillance Sensitivity and specificity of nceMRI and USS for HCC over 30 months of surveillance	Per round of surveillance analysis will be done for each visit: Baseline, visits 2, 3, 4, 5 and 6 For the 30 months of surveillance, analysis will be done for the entire 30 months of surveillance	
Secondary objectives				
To determine the stage and size of HCC at diagnosis and the number of indeterminate lesions detected		Numbers of HCC detected by nceMRI and USS at a very	At each 6 monthly surveillance round	

To determine the proportion of patients that receive treatment with curative intent	the Barcelona Clinic Liver Cancer staging system. The number and size of HCC tumours per participant with HCC The number of new indeterminate lesions identified at each surveillance round Proportion of participants diagnosed with HCC who go	At any time point an HCC is diagnosed, the analysis

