6. OBJECTIVES AND OUTCOME MEASURES

		Outcome Measures	Timepoint(s)
Primary Objective To evaluate the diagnostic non-contrast enhanced (no ultrasound scans (USS) as s for the diagnosis of hepato (HCC).	ceMRI) and surveillance tools	True positive tests for HCC per round of surveillance False positive tests for HCC per round of surveillance Positive predictive value for HCC per round of surveillance True negative tests for HCC over the 30 months of surveillance False negative tests for HCC over the 30 months of surveillance Sensitivity and specificity of nceMRI and USS for HCC over 30 months of surveillance	Per round of surveillance analysis will be done for each visit: Baseline, visits 2, 3, 4, 5 and 6 For the 30 months of surveillance, analysis will be done for the entire 30 months of surveillance
Secondary objectives			
To determine the stage an diagnosis and the number lesions detected		Numbers of HCC detected by nceMRI and USS at a very early, early, intermediate or advanced stage as defined by the Barcelona Clinic Liver Cancer staging system.	At each 6 monthly surveillance round (Baseline, visits 2, 3, 4, 5 and 6

To determine the proportion of patients that receive treatment with curative intent	The number and size of HCC tumours per participant with HCC The number of new indeterminate lesions identified at each surveillance round Proportion of participants diagnosed with HCC who go on to receive treatment with curative intent	At any time point an HCC is diagnosed, the analysis will be conducted once all participants complete the			
To evaluate the impact of the modality used for HCC surveillance on quality of life (QoL) and anxiety and depression	Results of the EQ-5D-5L questionnaire and Hospital Anxiety and Depression Scale questionnaire	study. At each 6 monthly surveillance round (Baseline, visits 2, 3, 4, 5 and 6			
To evaluate the participants' attitude, experience, and acceptability of nceMRI and USS for HCC surveillance	Results of participant experience questionnaire	Baseline, visit 5			
To evaluate the feasibility of nceMRI and USS as surveillance tools for HCC	Number of missed appointments (cancelled or missed), number of participants lost to follow-up, Number of participants where HCC surveillance is no longer indicated	At the end of the study			

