Participants that complete all 6 rounds of surveillance without a positive surveillance test and without HCC will undergo a contrast enhanced MRI at the end of the study (end of study ceMRI). The diagnostic allocation schedule will be modified for these scans as there will be no opportunity to follow-up LI-RADS 3 and 4 lesions. In these scans LI-RADS 1, 2 and 3 will be classed as not HCC and LI-RADS 4 and 5 lesions will be classed as HCC.

Follow-up for indeterminate lesions beyond 30 months

To enable potential future research, participant consent will be sought to allow follow-up through medical records or through data provided from NHS England, the NHS Central Register for Scotland and other patient registries for up to 10 years after their study participation is completed. This is to allow for collection of data relating to lesions that are still indeterminate at the end of 30 months surveillance period and to evaluate if those without HCC at the end of the study still go on to develop HCC. To facilitate this follow-up, personal identifiable information will be collected and stored centrally with participants' permissions.

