11.2. Description of the Statistical Methods

Statistical analysis for Primary outcome measure

Measures of diagnostic performance will be determined per round of surveillance and over the 30 months of study participation.

Diagnostic performance per round of surveillance

At each round of surveillance, the following data will be calculated and compared between USS and nceMRI.

- 1. Number and proportions of positive surveillance USS and nceMRI see section 9 for definitions of positive tests
- Number and proportions of true positive (TP) and false positive (FP) USS and nceMRI. As each positive test will be followed by a full contrast enhanced MRI, TP and FP tests per round of surveillance will be calculated
- 3. Positive predictive value (PPV) of USS and nceMRI

Diagnostic performance for the overall study period of 30 months

For the purpose of this analysis, each USS and nceMRI scan for each participant completing the study will be assigned only one of the 4 possible diagnostic categories of: true positive (TP) or false positive (FP), true negative (TN) and false negative (FN). The sum of TP, FP, TN and FN in this analysis will therefore be equal to the total number of participants completing the study. TP and FP will be determined at each visit as described above. TN and FN will be determined at the end of the study when participants undergo the reference standard ceMRI as part of the study protocol. FN results will also include those cases that present with HCC during the study without a prior positive test (interval cancers) or cases where both USS and nceMRI are negative tests but a ceMRI scan is triggered by an AFP>20. Cases that are initially FP may subsequently change diagnostic category. For this analysis, the diagnostic category which is applicable at the end of the study will be used. For example, if a finding initially classed as an FP develops into an HCC that was correctly identified by the surveillance tests, then the diagnostic test will be counted as a TP for this analysis.

Sensitivity and specificity estimates will be calculated separately for nceMRI and USS and compared. Statistical significance of the observed differences in sensitivity/specificity will be evaluated using the McNemar's test of paired proportions, with a two-tailed P-value <0.05 used as the significance criteria.

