Further, we will assess if specific individual-level factors are associated with the diagnostic performance of nceMRI and USS. These will include BMI, gender, age and underlying disease aetiology. For sensitivity, we will assess this by fitting a logistic regression model including all patients with HCC. The dependent variable will be detection via USS/nceMRI, whereas age/BMI and gender will be included as independent variables. Equivalent models will be fitted to determine factors associated with specificity, but this time confined to patients without HCC instead of patients with HCC. A further sensitivity analysis will be conducted in order to compare the sensitivity of nceMRI with USS depending on the USS visualisation scores.

Other considerations relevant to measuring the primary outcome

Alpha-fetoprotein

Alpha-fetoprotein will be measured as part of clinical care at each study visit. In the situation where both USS and nceMRI do not report suspicious lesions (test negative), a contrast enhanced MRI scan will still be needed if:

AFP \geq 20 ng/mL OR doubling of AFP (or more) OR increasing on two consecutive tests.

If an HCC is diagnosed on a ceMRI that was triggered by AFP thresholds rather than by USS / nceMRI, then both USS and nceMRI will be regarded as false negatives

Incidental findings:

Focal hepatic lesions: If an incidental finding is noted in the liver but no further imaging recommended (e.g. simple cysts), scans will be classed as test negative. Lesions in the liver, which are not thought to be HCC, but are considered to require imaging clarification with e.g. contrast-enhanced imaging, will be classed as test positive in the main study endpoint, but will be subject to a planned sensitivity analysis.

Cirrhosis-related complications: If a new ascites is identified on USS or MRI, this will be recorded (small, moderate and large volume). Other non-cancer complications of cirrhosis, such as development of features of portal hypertension, or venous thrombosis will be recorded for both tests.

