Extrahepatic: Extrahepatic incidental findings will be documented on the study proforma and assessed for likely significance. If a significant incidental finding is noted outside the liver this will be documented. Subsequent follow-up investigations will be recorded, as well as any significant diagnoses. Incidental findings in organs outside the liver will be managed according to local clinical routine, and not be counted as TP or FP when calculating sensitivity and specificity of nceMRI/USS.

Statistical analyses for secondary outcome measures

- 1. At each surveillance round, graphical methods will be used to analyse data for the numbers of:
 - a. very early, early, intermediate and advanced stage HCC as defined by the Barcelona Clinic Liver Cancer Staging system
 - b. the size and number of HCC, in TP cases
 - c. The number of new indeterminate lesions
- 2. Graphical methods will be used to analyse data on the number and proportions of participants with HCC who receive treatment with curative intent.
- 3. Quality of life and anxiety and depression: QoL will be assessed using the EQ-5D-5L questionnaire and anxiety and depression using the Hospital Anxiety and Depression Scale (HADS). Patients will be asked to complete the questionnaires at 6 monthly intervals to coincide with their visits for MRI / USS. Associations of the results from these questionnaires with other variables will be explored, particularly with HCC diagnosis and FP surveillance tests.
- 4. Acceptability of MRI and USS as surveillance tests: Patients will be asked to complete questionnaires documenting their experience of USS and MRI at the baseline visit and visit 5. These questionnaires have already been developed based on the questionnaires used in the METRIC study⁴¹, which assessed the acceptability of USS and MRI in patients with Crohn's disease. Scores derived from these questionnaires will constitute the outcome measure and they will be compared between nceMRI and USS.
- 5. Feasibility of nceMRI and USS as surveillance tools: To measure feasibility of nceMRI and USS as a surveillance tool, data will be collected on the number and reasons for missed scans. In particular we will determine if scans were cancelled by the hospital due to capacity issues, if the patient was lost to follow-up, or surveillance for HCC is no longer indicated. This data will be analysed using graphical methods.

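### HCC size and number are defined per participant with HCC but analysed only in true-positive cases, so cancers missed by both tests drop out of the display

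*Protocol*

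**What the plan says.** The secondary objective in the synopsis is "To determine the stage and size of HCC at diagnosis and the number of indeterminate lesions detected". One outcome measure under it, in section 6 and again in the synopsis, is "The number and size of HCC tumours per participant with HCC". Neither place limits this measure to cancers that a surveillance test found.

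Section 11.2, in item 1 of the secondary analyses, plans graphical displays at each surveillance round. Item 1a covers "very early, early, intermediate and advanced stage HCC as defined by the Barcelona Clinic Liver Cancer Staging system". Item 1b covers "the size and number of HCC, in TP cases".

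The primary analysis in section 11.2 fixes which cancers are not true positives (TP):

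- Interval cancers: "FN results will also include those cases that present with HCC during the study without a prior positive test (interval cancers".
- Cancers found on a contrast MRI (ceMRI) triggered by AFP when both tests were negative: "then both USS and nceMRI will be regarded as false negatives".
- Cancers found only at the closing scan: "TN and FN will be determined at the end of the study when participants undergo the reference standard ceMRI".

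For that closing scan, section 9.8.1 sets its own threshold: "In these scans LI-RADS 1, 2 and 3 will be classed as not HCC and LI-RADS 4 and 5 lesions will be classed as HCC".

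**The concern.** The outcome population and the analysis set differ by the protocol's own definitions. A participant whose cancer was missed by both ultrasound (USS) and non-contrast MRI (nceMRI) has HCC, and so belongs to the outcome. That participant is not a TP case, and so is absent from the only planned analysis of size and number. No other text brings those tumours back.

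Item 1b is also out of line with the rest of section 11.2. The curative-treatment display (item 2) covers participants with HCC, and the regression on sensitivity covers all patients with HCC. Item 1b alone selects explicitly on a positive test.

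Surveillance aims to find cancer while it is curable, so a reader will want to know how large and how numerous the missed cancers were. Following item 1b as written would not show this. The objective speaks of HCC at diagnosis, but the display would describe HCC given detection by the tests being evaluated.

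**Working it through.** **Inputs (section 11.3).** 50 HCCs; sensitivity 70–90% for nceMRI and 30–50% for USS; McNemar's test with 90% power and 5% type 1 error. Section 11.2 makes the test two-sided. The protocol states no correlation between the tests.

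**Step 1: reproduce Table 2.** With s the discordant proportion and d the difference in sensitivity,

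n = [1.960·√s + 1.282·√(s − d²)]² / d².

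For 80% versus 50% at a correlation of 0.1:

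- Both positive: 0.8×0.5 + 0.1×√(0.8×0.2×0.5×0.5) = 0.42.
- Discordant cells: 0.80 − 0.42 = 0.38 and 0.50 − 0.42 = 0.08, so s = 0.46 and d = 0.30.
- n = [1.960×0.678 + 1.282×0.608]² / 0.09 = 49.4, rounded up to 50. Table 2 gives 50.

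The same formula and correlation give all nine sensitivity cells exactly (31, 54, 116; 21, 30, 50; 14, 19, 27). They also give six of the seven numeric specificity cells; the seventh may be damaged in the text available. Independence gives 55 for the 80%/50% cell. A correlation of 0.1 is therefore inferred from Table 2 and remains an assumption.

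**Step 2: cancers missed by both tests.** These are lost from item 1b however TP is read.

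P(missed by both) = (1 − Se₁)(1 − Se₂) + ρ·√[Se₁(1 − Se₁)Se₂(1 − Se₂)].

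At the maximum positive correlation every cancer missed by nceMRI is also missed by USS, so P = 1 − Se of nceMRI.

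| nceMRI / USS | Independence | ρ = 0.1 | Maximum positive |
|---|---|---|---|
| 90% / 50% | 0.05 → 2.5 of 50 | 0.05 + 0.015 = 0.065 → 3.3 | 0.10 → 5 |
| 80% / 50% | 0.10 → 5.0 of 50 | 0.10 + 0.020 = 0.120 → 6.0 | 0.20 → 10 |
| 70% / 30% | 0.21 → 10.5 of 50 | 0.21 + 0.021 = 0.231 → 11.6 | 0.30 → 15 |

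The first and last rows bound the nine combinations in each column. With strong negative dependence the loss could fall to zero.

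**Step 3: if TP is read separately for each test.** The loss is then 50 × (1 − Se), which needs no correlation: 25 to 35 of 50 for USS and 5 to 15 of 50 for nceMRI. Section 11.8 adds a non-diagnostic route under this reading, because a test not performed at a visit where HCC is diagnosed is assigned as a false negative. The text does not say whether a TP case means positive on either test or on the test displayed.

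**The case against.** The best defence is the per-round structure. Item 1 is set at each surveillance round, and section 11.2 calculates only true and false positives per round, leaving false negatives to the end of the study. A per-round display of TP tumours fits that. This explains much of the restriction but does not remove the conflict: an AFP-triggered cancer is known at its round, one found on the closing ceMRI is known at visit 6, and the outcome carries no such limit.

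It is also fair that the analysis is secondary and graphical, that no test of size is planned, and that section 11.1 leaves detail to a statistical analysis plan. But the protocol itself names the analysis set, so a plan that follows it inherits the gap.

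Four stronger readings are tempting, and the documents do not support them:

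- **That the omission flatters both tests.** Missed cancers still count as false negatives in the 30-month sensitivity. Interval cancers might be larger and closing-scan cancers smaller than the rest; the documents fix no direction.
- **That stage and size would describe different cancers.** Item 1a has no TP limit, but section 6 words the stage outcome as HCCs detected by the two tests, so 1a can be read as covering the same set as 1b.
- **That a biased comparison of size between nceMRI and USS is planned.** Item 1b states no such comparison.
- **That most cancers leave the USS display.** That holds only under the per-test reading in step 3, which the text does not settle.

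**Conclusion.** The contradiction stands in the current text. Item 1b leaves out part of the population for which the protocol defines the outcome, and selects the remainder on detection. The loss that does not depend on how TP is read is the cancers missed by both tests: about 2.5 to 10.5 of 50 under independence, about 3 to 12 at a correlation of 0.1, and 5 to 15 at the maximum positive correlation. These figures rest on 50 HCCs and the assumed sensitivities in section 11.3. The per-test losses (25 to 35 for USS, 5 to 15 for nceMRI) are conditional on an unsettled reading. The effect is confined to the reported distribution of tumour size and number. The point is worth correcting before analysis, but it is not a threat to the study's main result.

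**What to change.** In section 11.2, item 1b, replace the TP restriction with: in all participants with HCC, by detection route (nceMRI only, USS only, both, neither), with the last group split into interval, AFP-triggered and end-of-study ceMRI.

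- Take size and number from the reference-standard diagnostic imaging or histology, so that one measurement serves both tests. Use hospital records for interval cancers.
- Show end-of-study LI-RADS 4 lesions separately. At that scan they count as HCC without follow-up, whereas during the study they are first treated as indeterminate.
- Keep the per-round TP display as a subset, and say whether TP there means positive on either test or on the test displayed.

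The cost is a few words and one extra grouping. The outcome as defined already calls for size and number in every participant with HCC, and section 9.11 continues collection from hospital records after an HCC diagnosis. However, section 9.8.2 does not list tumour size among the ceMRI proforma items it names, so its capture should be confirmed. Some size data for interval cancers diagnosed outside study scans may be incomplete; report how many are missing.

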To evaluate whether integration of nceMRI with clinical and laboratory variables can improve performance for HCC surveillance	Sensitivity and specificity of multivariable models for the diagnosis of HCC	End of study			
To perform a mechanistic study to use multiparametric quantitative MRI to assess the background liver in patients with cirrhosis.	Quantitative variables extracted from MRI data; T1 (ms), R2* (ms), PDFF (%), ADC (mm ² /s)	End of study			
To determine the long-term outcomes of study participants	A composite end point including the outcomes of: all cause mortality, liver related mortality, liver decompensation (ascites, hepatic encephalopathy, variceal bleeding), hepatocellular cancer, non primary liver cancer, liver transplantation	Up to 10 years after the last study MRI scan is performed			
Comparator – Reference standardThe reference standard will be diagnosis of HCC based on contrast enhanced CT/MRI or histology or by consensus in multi-disciplinary team meetings at the local liver clinic.					

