- 6. Multivariable algorithms: Demographic, laboratory and clinical data will be collected every 6 months including Child Pugh and Model for End-Stage Liver Disease (MELD) scores. Multivariate analysis will be used to assess if inclusion of nceMRI sequences and routinely available data or other biomarkers

improves diagnostic performance compared to USS. The multivariate models will be developed and reported according to the updated TRIPOD (Transparent Reporting of a multivariable prediction model for Individual Prognosis Or Diagnosis) statement⁴².

- 7. Mechanistic sub-study outcomes: Image processing of quantitative nceMRI and radiomics will be performed using semi-automated pipelines to study the "field effect". This will include:
 - a. automated liver segmentation using a convolution neural network, and manual definition of HCC;
 - b. creation of quantitative parameter maps from physical signal-models. We will perform model driven registration of DWI data to compute ADC and IVIM (D, D*, F) maps, quantify T1, R2*, and PDFF maps;
 - c. extraction of summary quantitative parameters and radiomics features in background liver parenchyma using a region growing algorithm progressively away from the defined HCC lesions
 - d. reporting the results in a standardised format and returning a table of imaging biomarkers for upload into the electronic data capture system.

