11.3. Sample Size Determination

Sample size calculations were performed to estimate a) the minimum number of HCCs and b) patients with cirrhosis and number of HCC needed to detect a difference in sensitivity and specificity between nceMRI and USS. Calculations used McNemar's test for paired proportions (power 90%, type 1 error at 5%). Based on literature, we assumed nceMRI and USS sensitivity of 70-90%⁴³ and 30-50%¹⁸ respectively, and nceMRI and USS specificity of 80%⁴³ and 90%¹⁸ respectively. The calculations suggest that in most scenarios, 50 HCCs and 200 controls would be sufficient to identify a difference in sensitivity/specificity.

Sensitivity		Ultrasound		
		se=30%	se=40%	se=50%
	se=70%	31	54	116
nceMRI	se=80%	21	30	50
	se=90%	14	19	27
Specificity		sp=90%	sp=95%	sp=98%
	sp=80%	244	96	61
nceMRI	sp=90%	NA	530	173
	sp=98%	173	2	NA

Table 2. Minimum number of participants required to demonstrate a statistically significant difference

 in sensitivity/specificity

To observe at least 50 HCCs, the cohort will be enriched with people with a risk of HCC of at least 3% per year (see section 9.4 also). This 3% per year threshold is derived from risk distribution observed among the first 1500 patients recruited to the Pearl cohort. Assuming there will be 2150 participants in Pearl at the time of AMULET inception, and assuming we will continue to see the same risk distribution in the
latter recruited patients as for the first 1500 patients, we determined that selecting patients with a 3year risk of >9% would give rise to 50 HCCs plus ~250-300 controls with liver cirrhosis and no HCC.

Figure 4. HCC risk distribution in Pearl – expected number of HCCs and non HCCs at a >3% annual HCC risk threshold

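### The combined nceMRI-plus-clinical model is compared only with USS, so a gain cannot be credited to integrating the clinical variables

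*Protocol*

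**What the plan says.** The objective, in the Synopsis and in section 6, is: "To evaluate whether integration of nceMRI with clinical and laboratory variables can improve performance for HCC surveillance". Its outcome measure is "Sensitivity and specificity of multivariable models for the diagnosis of HCC". Neither names what the model is to be compared with.

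Section 11.2, item 6 of the secondary analyses, does name a comparator: "Multivariate analysis will be used to assess if inclusion of nceMRI sequences and routinely available data or other biomarkers" "improves diagnostic performance compared to USS". Item 6 cites TRIPOD for developing and reporting the models. No part of the protocol states a comparison of the combined model with nceMRI alone, or with USS plus the same variables.

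nceMRI against USS is already the primary analysis: "Sensitivity and specificity estimates will be calculated separately for nceMRI and USS and compared", tested by "McNemar's test of paired proportions, with a two-tailed P-value <0.05 used as the significance criteria".

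**The concern.** An analysis of what integration contributes should hold the imaging test fixed and vary the added variables. Item 6 sets imaging plus variables on one side against a different imaging test without them on the other. The result is the sum of two effects: replacing USS by nceMRI, and adding clinical and laboratory data. Only the second is specific to this objective, and the stated contrast does not separate it from the first.

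At stake is how a secondary result is read. If nceMRI is more sensitive than USS, as planned, the combined model will tend to look better than USS on sensitivity whatever the clinical variables contribute. That could be taken as support for a more complex algorithm when no evidence for the added complexity has been produced.

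**Working it through.** **Inputs (section 11.3).** The text says "we assumed nceMRI and USS sensitivity of 70-90" per cent, with USS at 30-50%; specificity 80% for nceMRI and 90% for USS; about 50 HCCs; "Calculations used McNemar's test for paired proportions (power 90%, type 1 error at 5" per cent).

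**Step 1: reproduce the plan's own figures.** For paired proportions p1 and p2 with within-pair correlation r:

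- p11 = p1·p2 + r·√[p1(1−p1)p2(1−p2)]
- pd = p1 + p2 − 2·p11, and d = p1 − p2
- n = [1.96·√pd + 1.2816·√(pd − d²)]² / d²

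The protocol does not state r. With r = 0.1 (an assumption) the formula returns 15 of 15 usable cells of Table 2 exactly; with r = 0 only 4 of 15 fall within tolerance. Example, 80% vs 50%: p11 = 0.40 + 0.02 = 0.42; pd = 0.46; d = 0.30; n = (1.329 + 0.780)² / 0.09 = 49.4, so 50, as printed. The cell for 98% vs 95% specificity (printed as 2, formula 719) was left out because it may be damaged in the text available; it does not bear on this point.

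**Step 2: the gain over USS when the clinical variables add nothing.** The combined model then performs as nceMRI alone, and the gain over USS is nceMRI minus USS. In sensitivity points:

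| nceMRI | USS 30% | USS 40% | USS 50% |
|---|---|---|---|
| 70% | 40 | 30 | 20 |
| 80% | 50 | 40 | 30 |
| 90% | 60 | 50 | 40 |

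The range is 20 to 60 points. On specificity the same model is 80 − 90 = −10 points at the values assumed in the text. The other pairs in Table 2 run from 80 − 98 = −18 to 98 − 90 = +8.

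**Step 3: how often that model would beat USS on sensitivity.** Power = Φ{[|d|·√n − 1.96·√pd] / √(pd − d²)}, with n = 50 and r = 0.1.

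- 80% vs 50%: (2.121 − 1.329) / 0.608 = 1.30, power 90%.
- 80% vs 40%: (2.828 − 1.414) / 0.601 = 2.35, power 99%.
- Over the nine cells: from 56% (70% vs 50%) to above 99%.

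**Step 4: what the contrast with nceMRI alone could show.** Suppose the combined model finds extra HCCs and loses none, so that pd = d = gain g. For g = 0.10: (0.707 − 0.620) / 0.300 = 0.29, power 61%. For gains of 5, 15 and 20 points the same formula gives about 35%, 80% and 91%. Any losses reduce these figures. The normal approximation is itself rough here: a 10-point gain in 50 HCCs means about five discordant pairs, and five all in one direction give an exact two-sided p of 2 × 0.5⁵ = 0.0625.

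**The case against.** The strongest reply is that item 6 fits the objective. USS is the current standard for surveillance throughout the protocol, and the objective speaks of improving surveillance, so combined model versus USS is a legitimate question. This stands as a possible reading. A reader might infer that the protocol sets itself the task of improving on nceMRI alone and then contradicts itself, but the objective names no comparator and the documents do not support a contradiction. Because nceMRI versus USS has its own primary objective, added value is the more natural reading of a separate objective on integration; it remains an inference. Under either reading, a gain over USS does not measure what integration adds.

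Second, a reader might infer that the study is unable to answer the question, or that the combined model is bound to win. Neither follows. Participants are scheduled for both scans and clinical data at every visit, and sensitivity and specificity are planned outputs both for nceMRI and for the models; only the comparison between them is unstated. And at 80% against 90% specificity an uninformative model loses to USS on half of the outcome measure. Only the sensitivity gain is built in.

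Third, section 11.1 leaves details to the SAP. That covers the modelling technique, the performance metric and the method of internal validation. It does not cover the comparator, which the protocol itself fixes as USS.

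**Conclusion.** The point holds in a limited form. The objective names no comparator, item 6 names only USS, and the resulting contrast mixes the primary nceMRI-versus-USS difference with any contribution of the added variables. On the protocol's assumed sensitivities, 20 to 60 points of apparent gain over USS would be present with no contribution from the clinical variables, accompanied by 10 points lower specificity at the assumed values.

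The 20 to 60 points rest only on section 11.3 and on the premise that a model with uninformative additions performs as nceMRI alone. The power figures rest additionally on the assumed correlation of 0.1 and on 50 HCCs. The primary analysis, recruitment and data collection are unaffected; this is an inexpensive improvement to one secondary analysis.

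**What to change.** In section 11.2, item 6, and in the SAP, add nceMRI alone as a comparator alongside USS: in the same participants, report the difference between nceMRI plus clinical and laboratory variables and nceMRI alone, in sensitivity and specificity or in AUC, with a confidence interval and correction for optimism. Because item 6 speaks of nceMRI sequences as inputs, say whether nceMRI alone means the radiologist's read or a model using the sequences only. A comparison with USS plus the same variables would be a useful further addition.

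If the sponsor prefers to keep USS as the only comparator, restate the objective in the Synopsis and section 6 as combined model versus USS, and claim no added value from integration.

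The cost is about one sentence and no new data. The drawback is limited precision with about 50 HCCs (Step 4), so the contrast should be reported as an estimate with its interval; a non-significant result should not be read as evidence that the variables add nothing.
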